4.1.3.2 Sight-threatening Complications in the Fellow Eye (non-Study Eye)

Treatment of DME, PDR, or ASNV in the fellow eye may be conducted at any time and at the discretion of the Investigator (Section 6.8).

4.2 Scientific Rationale for Study Design

This is a randomized, sham-controlled, double-masked, multi-center, Phase 3 study to evaluate the efficacy and safety of intravitreal KSI-301 in participants with moderately severe to severe treatment-naïve NPDR. A randomized, double-masked design minimizes bias and is well-established for demonstrating the safety and efficacy of an investigational treatment. The rationale for other key design features is provided below.

4.2.1 Choice of Population

This study will enroll participants with moderately severe to severe NPDR (DRSS levels 47 and 53), who have not previously received intravitreal medications for DR in the study eye.

KSI-301 is being evaluated as a first-line anti-VEGF medicinal product to treat NPDR. Thus, participants must *not* have had prior use of an approved or investigational treatment (e.g., anti-VEGF or intraocular steroids) for DR in the Study Eye. Enrollment of participants who have not previously received intravitreal medications for DR in the study eye helps minimize biases inherent in the inclusion of participants who have failed prior lines of therapy.

Moderately severe to severe NPDR (DRSS levels 47 and 53) is a disease level that is most amenable to anti-VEGF therapeutic intervention (Ip 2012), while not meeting the threshold of alternative therapeutic interventions (e.g., panretinal photocoagulation in the case of proliferative DR) (Flaxel 2020). Additionally, and importantly, patients with moderately severe to severe NPDR are at higher risk of sight-threatening DR complications than patients with earlier stages of disease.

4.2.2 Choice of Sham Control

A sham comparator was selected for this trial to demonstrate that treatment with KSI-301 5 mg is superior to standard of care for NPDR, which includes standard-of-care therapeutics for treatment of the patient's underlying hyperglycemia, hyperlipidemia, and hypertension due to diabetes, as clinically indicated. Intravitreal anti-VEGF treatment has improved diabetic retinopathy and prevented disease progression in eyes with moderately severe to severe NPDR in patients without DME (Lim 2020). However, the regulatory status of intravitreal anti-VEGF has not been established as standard of care therapy for NPDR. For example, ranibizumab and aflibercept are both approved in the US for the treatment of DME and DR (NPDR and DR), however in Europe, only ranibizumab is approved for PDR, and neither is approved in Europe for NPDR. Furthermore, in the US where the intravitreal anti-VEGFs are approved for the treatment of adult patients with DR, they are not standard of care for NPDR (Flaxel 2020).

Hence, the choice of sham comparator does not deprive participants in the control group of access to accepted, standard-of-care therapy. As described in Section 4.1.3.1, all participants with progression of NPDR to the sight-threatening complications of DME, PDR, or ASNV will be identified and treated with KSI-301.

4.2.3 Choice of Primary Endpoint and Analysis

The primary endpoint, the proportion of eyes improving ≥ 2 steps on DRSS from baseline at Week 48, as measured using color fundus photographs graded by an independent, central reading center, was selected based on precedent for Phase 3 studies in NPDR (Lim 2020).

4.2.4 Choice of Duration of Treatment and Follow-up

The duration of treatment in this study will be approximately 92 weeks. The primary endpoint will be assessed at Week 48; secondary endpoints for efficacy will be assessed at Week 48, Week 96, and over time. These endpoints and associated duration of treatment were selected based on precedent for Phase 3 trials in NPDR (Lim 2020).

The choice of a safety follow-up interval of 8 weeks after the last dose is based on the expected duration of effect for KSI-301.

4.3 Justification for Dose

4.3.1 KSI-301 Dose Rationale

The durability of intravitreal anti-VEGF pharmacological effect is proportional to the dose and the half-life of the drug. A KSI-301 5 mg dose has approximately fold the equivalent molar dose of anti-VEGF binding capacity, at the time of injection, relative to aflibercept 2 mg. Preclinical modeling suggests that KSI-301 5 mg results in -fold the equivalent ocular concentration of aflibercept 2 mg three months after dosing. Both KSI-301 2.5 mg and KSI-301 5 mg that are being evaluated in the ongoing Phase 1b portion of Study KSI-CL-101 have not resulted in any dose limiting ocular or systemic toxicities and, as expected, have no clear dose-efficacy response relationship. Because the 5 mg dose of KSI-301 may have incrementally improved durability compared to the 2.5 mg dose, the 5 mg dose has been selected for this study. Interim efficacy data from the ongoing Phase 1b portion of Study KSI-CL-101 has thus far supported a prolonged dose regimen compared to other anti-VEGF medicinal products. The dosing regimen of KSI-301 5 mg intravitreal injection at Day 1, Week 8, Week 20, and every 24 weeks thereafter through Week 92 was selected in consideration of the increased durability of KSI-301 relative to existing intravitreal anti-VEGF therapies that have been studied in patients with NPDR.

The injection volume used to deliver a 5 mg dose has been well-tolerated in previous KSI-301 studies (additional information can be found in the IB) as well as in studies of
4.3.2 Sham Injection Rationale

Sham injections are used as a comparator to KSI-301 and to preserve study masking and minimize bias. Additional details are provided in Section 4.2.2.

4.4 End of Treatment

Participants may withdraw from the study at any time and for any reason without prejudice to their future medical care by the Investigator or at the study site. Every effort should be made to keep participants in the study. The reasons for end-of-treatment/early termination (ET) are provided in Section 7.0.

4.5 End of Study Definition

The end of the study is defined as the last follow-up visit of the last participant enrolled (i.e., the last enrolled participant's final visit) or a Sponsor decision to terminate the study, whichever comes first.

A participant is considered to have completed the study if he/she has completed all phases of the study, including the Week 100 safety follow-up assessment.

4.6 Treatment After End of Study

All participants will return to standard of care treatment, at the discretion of their treating physician, after completion of their final follow-up visit or once they discontinue from the study prematurely. The Sponsor will not provide continued access to study treatment following the end of the study or the end of each participant's study treatment period.

5.0 STUDY POPULATION

Participants will be randomized to a specified treatment group only if they meet all the inclusion criteria and none of the exclusion criteria.

Deviations from the inclusion and exclusion criteria are not allowed because they can potentially jeopardize the scientific integrity of the study, regulatory acceptability, or participant safety. Therefore, adherence to the criteria as specified in the protocol is essential. Prospective approval of protocol deviations to recruitment and enrollment criteria, also known as protocol waivers or exemptions, are not permitted.

Inclusion/exclusion criteria (Sections 5.1 and 5.2) will be assessed at Screening and on Day 1 to determine a participant's eligibility for the study. Instructions for participants who meet all eligibility criteria at the Screening visit but do not meet the BCVA and/or SD-OCT CST eligibility criteria when they return for the planned Day 1 visit are provided in Section 5.5.

5.1 Inclusion Criteria

Participants are eligible to be included in the study only if all the criteria in Sections 5.1.1 and 5.1.2 apply.

5.1.1 Ocular Inclusion Criteria

Where applicable, ocular inclusion criteria will be confirmed or assessed by the independent, masked image reading center.

- 1. Participants with moderately severe to severe NPDR in the Study Eye (DRSS levels 47 and 53 as determined by the reading center based on color fundus photographs), who have not previously received intravitreal medications for DR or DME, and in whom pan-retinal photocoagulation (PRP) can be safely deferred for at least 6 months per the Investigator.
- 2. BCVA ETDRS letter score in the Study Eye of ≥69 letters (approximate Snellen equivalent of 20/40 or better) in the Study Eye at Screening and confirmed at Day 1.

Only one eye per participant is eligible to participate in the study. If both eyes are eligible to become the Study Eye, the eye with worse BCVA and/or worse DR severity at Screening will be selected as the Study Eye. If both eyes are eligible and have the same BCVA and/or DR severity or one eye has worse BCVA and the fellow eye has worse DR, the decision of which eye to select as the Study Eye will be made by the Investigator.

5.1.2 General Inclusion Criteria

- 3. Male or female ≥ 18 years of age.
- 4. Capable of giving signed informed consent, as described in Appendix 1, which includes compliance with the protocols and restrictions listed in the informed consent form (ICF) and in this protocol.

- 5. Type 1 or 2 diabetes mellitus and HbA1c of $\leq 12\%$.
- 6. For women of childbearing potential: agreement to remain as abstinent (refrain from heterosexual intercourse) or use contraceptive methods that result in a failure rate of <1% per year during the treatment period and for at least 90 days after the last dose of study intervention.
 - A woman is considered of childbearing potential if she is post-menarchal, has not reached a post-menopausal state (≥12 months of amenorrhea with no identified cause other than menopause), and has not undergone surgical sterilization (removal of ovaries and/or uterus). The definition of childbearing potential may be adapted for alignment with local guidelines or requirements.
 - b. Examples of contraceptive methods with a failure rate of <1% per year include bilateral tubal ligation, male sterilization, established, proper use of hormonal contraceptives that inhibit ovulation, hormone-releasing intrauterine devices and copper intrauterine devices.
 - c. Contraception methods that do not result in a failure rate of <1% per year such as cap, diaphragm, or sponge with spermicide, or male or female condom with or without spermicide, are not acceptable.
 - d. The reliability of sexual abstinence should be evaluated in relation to the duration of the clinical trial and the preferred and usual lifestyle of the participant. Periodic abstinence (e.g., calendar, ovulation, symptothermal, or post-ovulation methods) and withdrawal are not acceptable methods of contraception.
- 7. For men: agreement to remain abstinent or use contraceptive measures and agreement to refrain from donating sperm, as defined below:
 - a. With female partners of childbearing potential, men must remain abstinent or use a condom plus an additional contraceptive method that together result in a failure rate of <1% per year during the treatment period and for at least

after the last dose of study intervention. Men must refrain from donating sperm during this same time period.

8. Ability and willingness to undertake all the scheduled visits and assessments.

5.2 Exclusion Criteria

Participants are excluded from the study if any of the criteria in Sections 5.2.1 or 5.2.2 apply.

5.2.1 Ocular Exclusion Criteria

Where applicable, ocular exclusion criteria will be determined by an independent, masked image reading center.

- 1. Presence of center-involved DME in the study eye, defined for this purpose as CST of \geq 320 microns on SD-OCT (Heidelberg Spectralis or equivalent value on other OCT instruments).
- 2. Prior PRP in the Study Eye.

- 3. Current anterior segment neovascularization (ASNV), vitreous hemorrhage, or tractional retinal detachment in the Study Eye.
- 4. Prior intravitreal anti-VEGF treatment in the Study Eye for DR or DME.
- 5. Prior intravitreal or periocular steroid in the Study Eye for DR or DME.
- 6. Prior use of an investigational intravitreal treatment for DR or DME in the Study Eye.
- 7. History of vitreoretinal surgery in the Study Eye
- 8. History of retinal detachment or treatment or surgery for retinal detachment in the Study Eye.
- 9. History of cataract surgery in the Study Eye within 2 months of screening.
- 10. History of YAG laser capsulotomy in the Study Eye within 2 months of screening.
- 11. Uncontrolled glaucoma (defined as intraocular pressure ≥25 mmHg despite treatment with antiglaucoma medication) in the Study Eye.
- 12. History of glaucoma-filtering surgery (trabeculectomy or tube shunt) in the Study Eye.
- 13. History of uveitis in either eye.
- 14. Significant media opacities, including cataract, in the Study Eye that might interfere with visual acuity, assessment of safety, OCT, or FP.
- 15. Cataract in the Study Eye that in the judgment of the Investigator is expected to require surgical extraction within 12 months of screening.
- 16. Aphakia in the Study Eye.
- 17. Active retinal disease other than the condition under investigation in the Study Eye.
- 18. Any history or evidence of a concurrent ocular condition present in the Study Eye, that in the opinion of the Investigator could require either medical or surgical intervention or alter visual acuity during the study (e.g., vitreomacular traction, epiretinal membrane).
- 19. Active or suspected ocular or periocular infection or inflammation in either eye at Day 1.
- 20. BCVA of hand motion or worse in the non-Study Eye or non-physical presence of a non-Study Eye (i.e., monocular).

5.2.2 General Exclusion Criteria

- 21. Women who are pregnant or lactating or intending to become pregnant during the study.
- 22. Women of child-bearing potential must have a negative urine pregnancy test result within 28 days prior to Day 1. If the urine pregnancy test is positive, it must be confirmed with a serum pregnancy test.
- 23. Uncontrolled blood pressure defined as a systolic value ≥180 mmHg or diastolic value ≥100 mmHg while at rest at Screening or on Day 1.

- If a participant's initial blood pressure measurement exceeds these values, up to two additional readings may be taken later the same day or on a different day during the screening period. If a participant's blood pressure is controlled by antihypertensive medications, the participant must be on a stable medication regimen continuously for 21 days prior to Day 1.
- 24. Kidney failure requiring renal transplant, hemodialysis or peritoneal dialysis or expected to require renal transplant, hemodialysis or peritoneal dialysis during the study.
- 25. Recent history (within the 6 months prior to screening) of myocardial infarction, stroke, transient ischemic attack, acute congestive heart failure, or any acute coronary event.
- 26. History of a medical condition that, in the judgment of the Investigator, would preclude scheduled study visits, completion of the study, or a safe administration of investigational product.
- 27. History of hypersensitivity to intravitreal agents such as aflibercept or ranibizumab or to any component of KSI-301, ophthalmic dye (fluorescein), dilating drops, or any of the anesthetic or antimicrobial preparations used during the study, as assessed by the Investigator.
- 28. Active cancer within the 12 months prior to Screening except for appropriately treated carcinoma in situ of the cervix, non-melanoma skin cancer, and prostate cancer with a Gleason score of <6 and stable prostate-specific antigen for >12 months.
- 29. Participation in an investigational study within 30 days prior to the screening visit that involved treatment with any investigational drug (excluding vitamins and minerals) or investigational devices, except for non-therapeutic ophthalmic imaging devices.

5.3 Lifestyle Considerations

No specific lifestyle restrictions are required.

5.4 Screen Failures

Screen failures are defined as participants who consent to participate in the clinical study but are not subsequently randomly assigned to study intervention. A minimal set of screen failure information is required to ensure transparent reporting of screen failure participants to meet the Consolidated Standards of Reporting Trials (CONSORT) publishing requirements and to respond to queries from regulatory authorities. Minimal information includes demography, screen failure details, eligibility criteria, and any serious adverse events (SAE) caused by a protocol-mandated intervention that occur during the screening period.

Participants who do not meet eligibility criteria within the 21-day screening period will not be eligible for randomization and will be considered 'screen-failed'. However, a participant may be rescreened up to one additional time at the discretion of the Investigator and in consultation with the Sponsor. When rescreening, the participant must be re-consented if more than 30 days have elapsed since the date of the last informed consent. In the event of rescreening, screening procedures need not be repeated if they fall within the 21-day screening window. If the rescreening occurs outside the 21-day window, all assessments performed at the initial screening

visit should be repeated during the re-screening visit except fluorescein angiogram (FA). If the rescreening visit is more than 8 weeks after the original screening visit, FA should be repeated. For a rescreening visit occurring fewer than 8 weeks after the original screening visit, although a new FA will not be required, the previously acquired FA will need to be re-submitted to the Reading Center labeled with the new participant number, along with the new screening images from the other modalities. This will ensure that all images from the participant are properly labeled, kept within the same directory and that eligible transmission numbers and audit trails are maintained.

When rescreening tests and procedures have been completed and results are available indicating the participant is eligible for study participation, the participant may be enrolled. When rescreening a participant, a new screening/enrollment number will be generated by IRT system to ensure there is an audit trail for the screen-failed participant.

5.5 Criteria for Temporarily Delaying Enrollment

Inclusion/Exclusion criteria will be assessed at Screening and on Day 1 to determine a participant's eligibility for the study.

If a participant meets all eligibility criteria (Sections 5.1 and 5.2) at the Screening visit but does not meet BCVA eligibility criteria due to expected variability and fluctuation in the BCVA when they return for the planned Day 1 visit, the Sponsor will allow the participant to return one additional time to reassess the BCVA, provided the assessment still occurs within the 21-day screening window. This repeat measurement for Day 1 visit (Repeat Day 1) is not considered a rescreen. Women of childbearing potential who return for a Repeat Day 1 Visit must have a negative pregnancy test during the Repeat Day 1 Visit (i.e., the pregnancy test must be performed and documented as negative on the same day as randomization/first injection). Day 1 and Repeat Day 1 Visit data shall be used/entered in the eCRF and IRT as follows:

- eCRF: In the event that a participant has a Repeat Day 1 Visit, data from assessments conducted at the planned randomization (Day 1) visit shall be clearly documented in the participant's source data. If the participant meets the eligibility criteria at the Repeat Day 1 visit, all data for assessments performed at that visit are entered into the eCRF under Day 1 and the original non-qualifying data will be entered as Unscheduled Visit assessments.
- IRT: In the event that a participant has a Repeat Day 1 Visit and is eligible for this study, the BCVA and SD OCT values from the Repeat Day 1 visit must be used for participant randomization into the IRT system. If the participant *does not* meet eligibility at the Repeat Day 1 visit, the participant must be recorded as a screen failure (Section 5.4) in the IRT system at that time.

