2.0 STUDY OBJECTIVES AND ENDPOINTS

Table 1 lists the primary, key secondary and additional secondary study objectives, along with their corresponding endpoints.

Table 1: Objectives and Endpoints

Table 1: Objectives and Endpoints Objectives	Corresponding Endpoints
	Corresponding Endpoints
Primary To demonstrate that KSI-301 5 mg is superior to sham treatment, with respect to proportion of eyes improving ≥2 steps on Diabetic Retinopathy Severity Scale (DRSS) from baseline at Week 48.	• The proportion of eyes improving ≥2 steps on DRSS from baseline at Week 48.
Key Secondary	
To demonstrate that KSI-301 5 mg is superior to sham treatment, with respect to proportion of eyes with vision-threatening complications of diabetes, and proportion of eyes improving \geq 3 steps on Diabetic Retinopathy Severity Scale (DRSS).	 Proportion of eyes developing any of the following from baseline through Week 48: PDR or ASNV; Vitreous hemorrhage or tractional retinal detachment believed to be due to PDR; or DME.
	• Proportion of eyes improving ≥3 steps on DRSS from baseline at Week 48.
	• Proportion of eyes developing PDR through Week 48.
Additional Secondary	
To evaluate the efficacy of KSI-301 5 mg compared to sham treatment.	• Proportion of eyes developing PDR or ASNV from baseline through Week 48.
	• Proportion of eyes developing vitreous hemorrhage or tractional retinal detachment, believed to be due to PDR, from baseline through Week 48.
	• Proportion of eyes developing DME from baseline through Week 48.
	• Proportion of eyes with a ≥2-step worsening from baseline on DRSS from baseline at Week 48.
	• Proportion of eyes with a ≥3-step worsening from baseline on DRSS from baseline at Week 48.
	• Time to first development of PDR, ASNV, or DME through Week 48.
	• Time to first development of PDR or ASNV through Week 48.
	• Time to first development of vitreous hemorrhage or tractional retinal detachment, believed to be due to PDR through Week 48.
	• Time to first development of DME through Week 48.
	• Mean change in SD-OCT central subfield thickness (CST) from baseline by visit over time.
	• Mean change in BCVA from baseline by visit over time.
	• Proportion of eyes who lose ≥ 5 , ≥ 10 , or ≥ 15 letters in BCVA from baseline by visit over time.

KS301P106 SAP Version 1.0 KSI-301 – Kodiak Sciences Inc.

Objectives	Corresponding Endpoints
To evaluate the safety and tolerability of KSI-301	Incidence of ocular and systemic adverse events up to Week 48.

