5.3 Study Definitions and Derived Variables

Unless otherwise specified, the duration of Week 48 analysis is defined as Study Day 1 until Week 48, as it is meant to be inclusive both of study treatments leading to the primary efficacy outcome at Week 48 and of safety assessments in that period.

Baseline values are defined as the most recent values prior to the first dose of study treatment.

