7.3 Additional Secondary Efficacy Analyses

As specified in Section 4.0, the Primary Analysis will evaluate the efficacy of KSI-301 compared to sham from Day 1 up to Week 48.

Table 4 lists the additional secondary efficacy endpoints, efficacy variable derivations, reporting statistics and analysis methods for the Primary Analysis and until the end of study.

Binary secondary efficacy endpoints will utilize the Cochran-Mantel-Haenszel (CMH) method stratified by the randomization stratification factors (i.e. baseline DRSS level and HbA1c level).

Time to event endpoints will be analyzed using the Kaplan-Meier estimates. The number of observations censored will be provided for each treatment group. The 50th percentile of Kaplan-Meier estimates will be used to estimate the median time to first event in each treatment group. A 2-sided 95% CI will be provided for the estimates. A log-rank test stratified by the randomization stratification factors (i.e. baseline DRSS level and HbA1c level) will be performed to compare the survival distributions between the treatments. The hazard ratio and its 95% CI will be reported from a Cox regression model stratified by the same randomization stratification factors with treatment as the covariate. For patients not known to have had an event at the time of the analysis data cutoff, the time will be censored at the date of the last scheduled study visit at analysis data cutoff.

Continuous endpoints (e.g. mean change from baseline in BCVA) will utilize a Mixed Model for Repeated Measures (MMRM). The model assumes missing at random (MAR). The model will include the change from baseline value as the dependent variable; categorical covariates of treatment group, protocol scheduled visit, treatment × visit interaction, and the randomization stratification factors (i.e. baseline DRSS level and HbA1c level) as well as continuous covariate of baseline BCVA, as fixed effects; and then subject as a random effect. Within-subject correlations will be assumed to follow an unstructured covariance matrix. If the model assuming an unstructured covariance matrix does not converge, a heterogeneous compound symmetry structure or an AR(1) covariance structure will be fitted.

For all additional secondary efficacy endpoints, data after the occurrence of intercurrent event will be censored, and missing and non-gradable data will not be imputed. Only observed, gradable and non-censored data will be used for analysis.

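### The BCVA model adjusts for one pre-dose reading although every participant has at least two; adding Screening BCVA as a second covariate would gain a little precision at almost no cost

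*Protocol*

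**What the plan says.** Protocol 5.1.1 sets the entry rule as "BCVA ETDRS letter score in the Study Eye of ≥69 letters", to be met "in the Study Eye at Screening and confirmed at Day 1". The schedule of activities (SoA-A) has BCVA at both visits, so every participant has two pre-dose readings.

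Protocol 5.5 covers a participant who passes at Screening but falls short on Day 1 through ordinary fluctuation: "the Sponsor will allow the participant to return one additional time to reassess the BCVA". A time limit applies to this second attempt: "provided the assessment still occurs within the 21-day screening window". If the repeat passes, "all data for assessments performed at that visit are entered into the eCRF under Day 1 and the original non-qualifying data will be entered", namely among the unscheduled assessments. The failed reading is therefore kept in the database, but not under the Day 1 label.

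SAP 5.3 states: "Baseline values are defined as the most recent values prior to the first dose of study treatment". For BCVA this is the Day 1 reading or, where there was one, the passing repeat.

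Two groups of endpoints rest on that value. The first is "Mean change in BCVA from baseline by visit over time", analysed by a mixed model with "continuous covariate of baseline BCVA, as fixed effects". The second is the proportions losing at least 5, 10 or 15 letters, analysed by the CMH method on the randomization strata with no adjustment for BCVA. SAP 2.0 and Table 4 class both as additional secondary. Neither document uses the Screening BCVA or a failed Day 1 BCVA in any analysis.

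**The concern.** A single acuity reading carries measurement error, and protocol 5.5 accepts this by allowing a repeat for fluctuation. A covariate measured with error explains less of the outcome than the true value would. A second reading, taken within the 21-day screening period and before randomization, holds further information on the same quantity. Leaving it out makes the residual variance of the BCVA model larger than it need be.

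What is at stake is the width of the confidence interval for the treatment difference in mean BCVA change. Validity is not at issue: both readings precede randomization, so the model with one covariate is unbiased for the treatment difference, and so is the model with two.

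**Working it through.** **Figures in the plan.** There is none to reproduce for BCVA. The sample size of about 240 (120 per arm) was set for the DRSS endpoint, and its response rates and dropout rate are redacted. The documents give no mean, SD or test-retest error for BCVA, so the inputs below are assumptions and the results are ranges.

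**Assumptions.** True BCVA before selection is normal with mean and SD (76, 8), (78, 7), (80, 6) or (82, 5). Reading errors are independent with SD σ = 2, 3, 4 or 5 letters. True change to a later visit has SD δ = 5. Let τ be the SD of true BCVA.

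**Step 1: precision, closed form, ignoring the entry floor.** For one post-baseline visit:

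- one covariate: V1 = τ²σ²/(τ²+σ²) + δ² + σ²
- two covariates: V2 = τ²(σ²/2)/(τ²+σ²/2) + δ² + σ²

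With τ = 7, σ = 3, δ = 5:

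- V1 = 49×9/58 + 25 + 9 = 7.60 + 34 = 41.60
- V2 = 49×4.5/53.5 + 34 = 4.12 + 34 = 38.12
- Variance reduction: 1 − 38.12/41.60 = 8.4%
- CI narrowing: 1 − √(38.12/41.60) = 4.3%
- Equivalent extra participants: 41.60/38.12 − 1 = 9.1%

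**Step 2: the same with the entry rule.** I simulated 2,000,000 eyes per scenario with rounded readings: Screening at least 69 and Day 1 at least 69, or one repeat at least 69. I then fitted the change score on the planned baseline, without and with Screening BCVA. For (78, 7):

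| σ | V1 | V2 | Variance cut | CI narrower | Extra participants |
|---|---|---|---|---|---|
| 2 | 32.81 | 31.09 | 5.2% | 2.7% | 5.5% |
| 3 | 41.48 | 38.29 | 7.7% | 3.9% | 8.3% |
| 4 | 52.81 | 48.23 | 8.7% | 4.4% | 9.5% |
| 5 | 65.84 | 60.38 | 8.3% | 4.2% | 9.0% |

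Over all 16 scenarios the variance cut is 5.0 to 9.1%, the narrowing 2.5 to 4.7% and the equivalent gain 5.2 to 10.0%. On 240 participants, 5 to 10% is 12 to 24. With δ = 0 the gain would be larger, but no true change at all is unrealistic.

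**Step 3: how much the Repeat Day 1 rule contributes.** In the same simulation:

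- Repeat eyes are about 0.2 to 7% of entrants.
- The planned baseline is too high by 0.01 to 0.8 letters over all entrants. It is too high by 0.01 to 0.7 letters in eyes that never repeated, so most of the shift comes from the entry floor of 69.
- With no true change, a false loss of 5 letters or more at (78, 7), σ = 3 occurs in 15.1% of non-repeat eyes and 20.9% of repeat eyes, and repeat eyes are 2.8% of entrants. Their contribution to the overall rate is 0.028 × (20.9 − 15.1) = 0.16 percentage points.
- The largest contribution, at (76, 8), σ = 5, is 0.071 × (37.1 − 28.9) = 0.58 percentage points.

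**Step 4: the mean of all pre-dose readings as baseline for letter loss.** The overall false rate for 5 letters or more falls from about 6 to 29% to about 3 to 25%. Part of the fall, about one percentage point, arises only because averages fall on half letters. In repeat eyes the mean baseline error moves from between +0.7 and +2.5 letters to between −0.1 and −2.3, because a reading selected for being low now enters the mean. At (82, 5), σ = 5 it goes from +1.2 to −2.3, which is larger in size.

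**The case against.** The last value before dosing is the usual baseline, stated in advance and applied to all variables. The two documents do not conflict on it and no analysis is invalid. BCVA change lies outside the hierarchical family in SAP 7.2, and the trial was sized on DRSS. SAP 3.1 records that the sponsor has ended development of the product. A confidence interval 2.5 to 5% narrower will change no confirmatory decision, and its size rests wholly on assumed variability.

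All of that stands, and it makes this an optional improvement rather than a defect. It does not remove the point: the Screening reading is already in the database, and using it costs almost nothing.

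A reader might infer more from protocol 5.5: that letting a passing repeat replace a failed reading biases the BCVA results upward in a way that matters. The documents do not support that. The selection takes place before randomization and is expected to be equal in both arms, and the model already adjusts for baseline BCVA. What moves is the absolute letter-loss rate within each arm, by at most about 0.6 percentage points from this rule at the 5-letter threshold under the assumptions used.

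**Conclusion.** The point holds as a modest loss of precision in one additional secondary analysis. Using Screening BCVA as well as the Day 1 value would cut residual variance by about 5 to 9% and narrow the confidence interval by about 2.5 to 5%, equivalent to about 5 to 10% more participants for this endpoint. These figures assume a reading SD of 2 to 5 letters, a true-change SD of 5, independent reading errors and a single-visit approximation to the mixed model. The direction was the same in every scenario tried.

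No treatment comparison is biased and the primary DRSS test is not involved. It would also go too far to replace the planned baseline for the letter-loss proportions by an average: that reduces noise overall but reverses the error in repeat eyes, sometimes to a larger size. Such an average is defensible only as a sensitivity analysis.

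**What to change.** **Main change.** In SAP 7.3 and the BCVA row of Table 4, add Study Eye BCVA at Screening as a second continuous covariate beside the Day 1 baseline. The baseline definition in SAP 5.3 and the change score stay as they are. For rescreened participants, name the reading from the screening episode that led to randomization. Protocol 5.4 assigns them a new number and lets assessments still inside the 21-day window stand, so that reading may be filed under the former number.

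**Optional, sensitivity only.** Repeat the proportions losing at least 5, 10 or 15 letters with the mean of all pre-dose Study Eye readings as baseline. State expressly that a failed Day 1 reading filed as unscheduled is included, because a filter on scheduled visits would drop it. State also that the mean somewhat understates baseline in repeat eyes.

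**Cost.** A sentence or two in the SAP and minor programming, settled before unmasking. No new data are needed, and eligibility, visits and the DME definition, which refers to Day 1 BCVA, are untouched. The main change does nothing for the letter-loss proportions.
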